## **Study design and participants**

We prospectively enrolled children 24 months and younger and pregnant women from a rural community in the Mewat region located within the state of Haryana, India from July 11, 2016 to July 20, 2017. Recruitment and follow up were performed concurrently, though the recruitment target was met on February 11, 2017. The study was administered by Bal Umang Drishya Sanstha (BUDS), a New Delhi based non-profit organization with a focus on child health. This study was approved by the Research Ethics Committees of BUDS, New Delhi, India and the Johns Hopkins University, Baltimore, MD, USA. This trial is registered with ClinicalTrials.gov, number NCT03180138.

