## **Study Procedures**

An encrypted, cloud-based software platform developed by Royal Datamatics Pvt Ltd (RDPL), New Delhi, India was used for record keeping and delivery of automated mobile-phone reminders and compliance-linked incentives (Supplementary Figure 1). Any child 24 months or younger at the time of enrollment, with a mobile-phone in the household and the ability of their caregiver to provide written informed consent were considered eligible for this study. After obtaining written informed consent from the caregiver, basic demographic information, Global Positioning System (GPS)-location and caregiver's finger biometrics were collected. While the standard of care in this setting involves the use of written immunization records (cards and records at the local primary health center) and verbal notification of follow up visits, record keeping for all groups in this study, including the control group, was performed using the software platform. Eligible subjects were randomly assigned to one of three study groups: self-returns with software platform for record keeping (control), automated mobile-phone reminders alone, and automated reminders with compliance-linked incentives in the form of mobile-phone talk-time. At the time of enrollment, data on prior immunizations received by the child were obtained from government-issued immunization cards provided by the families. If cards were unavailable or lost, immunization records were verified using written records at the local primary health center. The government-run National Immunization program (Supplementary Table 1) provided and administered the immunizations. The date for the next scheduled immunization visit was provided at each follow up by the government staff and entered into the software platform by the field workers. Each follow up visit was also correlated with the scheduled return date (if recorded in the system) of the administered immunization. Since finger identification is unreliable in young children, the child's name along with their caregiver's fingerprint was used to ensure positive identification of individual children at every visit. The GPS coordinates (longitude and latitude) were also recorded at recruitment and at each follow up visit. All users (field staff and study team) were identified and logged onto the software platform using biometric identification. For the study groups receiving automated reminders, Short Message Service (SMS) in the local language (Hindi) were sent. At follow up visits, mobile-phone minutes equivalent to INR 30 (~USD 0.5) per completed immunization were provided in the compliance-linked incentives group. The amount of incentive was determined after input from the local investigators as well as the community workers. All data transfers and compliance-linked incentives transactions were automated and occurred in real-time.

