## **End Points**

Immunization coverage was the primary outcome of the study and was calculated for each child as the proportion of the total number of immunizations received divided by the total number of immunizations required at the time of measurement (i.e. at enrollment, end of study, etc.). We also calculated the cost in mobile-phone messaging and compliance-linked incentives. Timeliness of immunizations was a secondary outcome measure and was defined as the proportion of immunizations administered before or within 14 days after the scheduled date recorded during the study.

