## Statistical Analysis Plan

*Sample size:* Prior to the study, we anticipated that our best intervention would increase the baseline immunization coverage by least 20% compared to the control group. Assuming up to a 20% exclusion rate, we calculated that a sample of size 175 per group would yield us 90% power at 5% level of significance for this outcome.

*Statistical analysis:* Baseline data across the three study groups was summarized using either median and interquartile range (IQR) or frequencies and percentages. Multivariable Poisson regression analysis was used to estimate adjusted immunization rates in the two test study groups with the control group as reference. To compare immunization coverage at enrollment and at the end of the study, the incidence rate ratio was calculated accounting for median patient days in the study and the number of subjects for each intervention group. Unadjusted immunization coverage for each study group was calculated with Poisson exact 95% confidence intervals. Multivariable Poisson regression analysis was used to estimate adjusted immunization rates in the two test study groups with the control group as reference. Comparison between groups for timeliness of immunization was calculated using the Fisher-exact test. Data analysis was performed using Stata Version 14 (StataCorp LLC, College Station, TX USA) or GraphPad Prism Version 6.05 (La Jolla, CA 92037 USA).

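### The enrolment-to-end incidence rate ratio is built from group-level inputs that cannot use the within-child pairing, and the plan names no variance method for it

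*Combined protocol and SAP*

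**What the plan says.** The Statistical analysis paragraph of the Statistical Analysis Plan gives the purpose of this ratio, "To compare immunization coverage at enrollment and at the end of the study", and its construction: "the incidence rate ratio was calculated accounting for median patient days in the study and the number of subjects for each intervention group". It states no standard error, interval or test for the ratio. The only interval method it names belongs to a different quantity: "Unadjusted immunization coverage for each study group was calculated with Poisson exact 95% confidence intervals". No paired, clustered or robust method is mentioned.

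End Points defines a child's coverage in these words: "proportion of the total number of immunizations received divided by the total number of immunizations required at the time of measurement". It gives enrolment and end of study as examples of measurement times. Study Procedures says that at enrolment "data on prior immunizations received by the child were obtained from government-issued immunization cards", with health-centre records as the fallback. The numerator is therefore cumulative at both dates and is known for each child.

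The same SAP paragraph separately plans a multivariable Poisson regression of each test group against control. Its covariates are not listed, so the reader cannot tell whether enrolment coverage is among them.

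**The concern.** Every dose counted for a child at enrolment is counted again for that child at the end. The two totals are thus nested: end total = enrolment total + new doses. Median days and a headcount are summaries of an arm, and neither carries the link between a child's two values. A rate ratio computed from such inputs would by default take the variance for two unrelated Poisson samples, which leaves out the covariance between the totals.

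A second issue does not depend on the variance. The ratio is a before-after contrast within an arm. Children age, more doses fall due and doses accumulate in every arm, control included. A within-arm rise therefore does not by itself measure the effect of reminders or incentives. Randomisation protects only the comparison between arms.

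At stake are the precision reported for the change in coverage, which is the primary outcome measured at two dates, and how a reader interprets that change.

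**Working it through.** **1. The plan's own figure.** The one design figure is 175 per group with up to 20% excluded. With an assumed 40% versus 60% coverage, two-sided 5%, 90% power and a continuity correction, the two-proportion formula gives 140, and 140/(1 − 0.20) = 175. This supplies a number of children and nothing more. The documents give no dose count, coverage value, median follow-up, rate ratio or interval, so the dose numbers below are assumptions.

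**2. Variance with and without nesting.** Let B = doses at enrolment, N = new doses, E = B + N and R = E/B, all totals for an arm.

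- Two independent Poisson counts: Var(log R) = 1/B + 1/E.
- Nested counts, Poisson, new doses independent of prior doses (delta method on log(1 + N/B)): Var(log R) = (N/E)²(1/N + 1/B) = N/(B·E) = 1/B − 1/E.
- Ratio of interval widths on the log scale: √[(R + 1)/(R − 1)]. The number of children cancels.

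Example with 140 children, 6 prior and 3 new doses each: B = 840, N = 420, E = 1,260.

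- Independent: √(1/840 + 1/1260) = 0.0445.
- Nested: √(1/840 − 1/1260) = 0.0199.
- Width ratio: 2.24.

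| R | Width ratio |
|---|---|
| 1.10 | 4.58 |
| 1.25 | 3.00 |
| 1.50 | 2.24 |
| 1.67 | 2.00 |
| 2.0 | 1.73 |
| 3.0 | 1.41 |

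Over 4 to 8 prior and 1 to 4 new doses, the factor runs from √3 = 1.73 (4 prior, 4 new) to √17 = 4.12 (8 prior, 1 new).

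**3. Extra variation between children.** Enrolment takes "Any child 24 months or younger at the time of enrollment", so prior doses differ widely between children. Follow-up differs too: "Recruitment and follow up were performed concurrently, though the recruitment target was met on February 11, 2017". With the study ending on 20 July 2017, enrolment dates from 11 July 2016 to 11 February 2017 imply 374 to 159 days. Suppose prior and new doses each carry independent gamma variation of shape k, with no cap, and means b and m per child. The true variance per child is then (m/(b + m))²(1/m + 1/b + 2/k), against 1/b + 1/(b + m) under independence. With b = 6:

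- m = 3, k = 2: true 0.167, independent 0.278, width ratio √(0.278/0.167) = 1.29.
- m = 3, k = 1: true 0.278, independent 0.278, width ratio 1.00.
- m = 6, k = 2: true 0.333, independent 0.250, width ratio 0.87.

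Strong uncapped variation can therefore cancel the effect or reverse it.

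**4. Doses capped by a schedule.** A child cannot receive more doses than the schedule holds, which limits that variation. Simulations used ages 0–12 or 0–24 months and gave these width ratios:

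- 18-dose schedule, 3 to 9 months of follow-up, enrolment coverage 40% or 60%, 175 children: 1.2 to 2.5 for the ratio of counts, 1.3 to 2.4 for the ratio of coverages.
- 12- or 18-dose schedule, 159–374 days, 140 children, uptake stable within a child: 1.5 to 2.2 for counts, 2.4 to 4.7 for coverages.
- The same, with uptake redrawn after enrolment so that pairing is weakened: 1.2 to 2.2 for counts, 1.5 to 4.3 for coverages.

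No capped scenario fell below 1.

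**The case against.** The strongest reply is that this is an under-specified plan and not a demonstrated error. A reader might infer that the trial treated the two counts as independent, and that its interval is therefore two to three times too wide. The documents support neither. They name no variance method for this ratio, so independence is the default reading and not a stated choice. A factor of two to three needs R between about 1.25 and 1.67 with no extra variation between children, and neither condition is given. Even the direction is conditional, as step 3 shows.

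The sentence can also be read differently. Patient days in the study are zero at enrolment, so they cannot be the exposure for the enrolment count. If the ratio in fact compares new doses per patient-day, or compares groups, the counts are not nested and the variance argument falls away. Against this, the stated purpose is enrolment versus end of study. The ambiguity is itself a reason to rewrite the sentence.

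A reader might further infer that arms will be judged by which before-after test reaches 5%. Nothing in the plan says so, nor does it call this ratio the main result. The Poisson regression against control is the between-arm analysis. An interval that is too wide would also be conservative for the within-arm result.

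These points limit the claim. What stands is that the stated inputs cannot use the pairing, that no variance method is given, and that the before-after ratio is not marked as descriptive.

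**Conclusion.** The concern holds in a limited form. The stated construction cannot use the within-child pairing, and an interval for two independent Poisson counts would be calculated from the wrong variance. In the capped-dose models it would be too wide by about 1.2 to 4 times, with a few coverage-ratio scenarios slightly above 4. That range rests on assumed schedules, ages, follow-up and uptake. It also assumes that the ratio compares cumulative counts at the two dates. Under very strong uncapped variation the interval could be about right or too narrow, so no single factor should be quoted for this trial. Separately, and whatever the variance, the within-arm ratio is not a randomised comparison. The change is worth making because it is nearly free. It does not impugn the planned regression against control.

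**What to change.** Replace the group-level ratio in the Statistical analysis paragraph with the following:

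- Compute each child's coverage at enrolment and at end of study, each on the doses required at that date.
- Show within-arm change descriptively, with an interval that keeps each child's two values together (bootstrap by child, or cluster-robust by child).
- Base conclusions on each active arm against control, using either change in coverage or end coverage adjusted for enrolment coverage, with child-level robust standard errors. Name one of the two as the analysis. If the planned Poisson regression is to serve, say whether enrolment coverage enters it.

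If a rate ratio is kept, state what its two rates are, which exposure each uses and how its interval is formed.

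The cost is SAP wording and a few lines of code. The platform holds the immunization records for each child, so no new data are needed.

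### Poisson exact 95% intervals do not suit a primary outcome that is a bounded proportion per child, and no child-level variance is stated for the Poisson regression

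*Combined protocol and SAP*

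**What the plan says.** The End Points section makes immunization coverage the primary outcome, "calculated for each child as the proportion of the total number of immunizations received divided by the total number of immunizations required". The child is the unit and the value lies between 0 and 1.

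The Statistical Analysis Plan section gives the arm-level summary: "Unadjusted immunization coverage for each study group was calculated with Poisson exact 95% confidence intervals". It does not say which count the interval is built on. For the comparison of arms it says "Multivariable Poisson regression analysis was used to estimate adjusted immunization rates in the two test study groups with the control group as reference", a sentence that appears twice. No offset, covariate list, dispersion term, or robust or clustered variance is given there or elsewhere.

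Study Procedures admits "Any child 24 months or younger at the time of enrollment", so the number of immunizations required differs between children.

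**The concern.** A Poisson exact interval takes a single count of independent events whose variance equals its mean and which has no upper limit. A group's mean of child proportions is not such a count. The natural reading is that received doses were pooled by arm and divided by required doses. That ignores two features of the outcome:

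- **The ceiling.** A child cannot receive more than 100% of the required doses, so the variance is smaller than Poisson.
- **Within-child correlation.** One caregiver and one visit schedule govern all of a child's doses, so they tend to be received or missed together, and the variance is larger.

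The errors run in opposite directions, and nothing in the plan tells a reader which dominates. The published intervals for the primary outcome could overstate or understate precision. If the regression relied on default errors, the tests between arms could reject too often or too rarely.

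A lesser point is that pooling weights each child by the number of required doses, so the pooled ratio need not equal the mean of the child proportions.

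**Working it through.** **Inputs.** The plan gives 175 children per group with up to 20% excluded, so 175 × 0.80 = 140 analysable per arm. It gives no interval to reproduce. Coverage p, required doses per child m, and the within-child correlation ICC are not stated. They are assumed over ranges: p 0.4 to 0.9, m 8 to 12, ICC 0 to 0.5 unless noted.

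**Step 1: variance of pooled coverage.** With N children and m required doses each:

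- Poisson variance: p/(Nm)
- True variance: p(1−p)[1+(m−1)ICC]/(Nm)
- Ratio, true to Poisson: (1−p)[1+(m−1)ICC]

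Example: at p = 0.4, m = 12, ICC = 0.3, the ratio is 0.6 × (1 + 11 × 0.3) = 0.6 × 4.3 = 2.58, and the SE ratio is √2.58 = 1.61.

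The two effects cancel when ICC = p/[(1−p)(m−1)]. At p = 0.4 this is 0.667/11 = 0.06 for m = 12 and 0.667/7 = 0.10 for m = 8.

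| Coverage | True SE / Poisson SE, ICC 0 | ICC 0.3 (m = 8 to 12) | ICC at which errors cancel |
|---|---|---|---|
| 40% | 0.77 | 1.36 to 1.61 | 0.06 to 0.10 |
| 60% | 0.63 | 1.11 to 1.31 | 0.14 to 0.21 |
| 80% | 0.45 | 0.79 to 0.93 | 0.36 to 0.57 |
| 90% | 0.32 | 0.56 to 0.66 | 9/11 = 0.82 (m = 12); never (m = 8) |

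Below 1 the Poisson interval is too wide; above 1 it is too narrow. At 90% coverage and ICC 0.7 with m = 12, the SE ratio is √(0.1 × 8.7) = 0.93, still too wide.

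**Step 2: actual intervals.** Take N = 140 and m = 10, so 1,400 required doses. At p = 0.5 the Poisson exact interval is 0.464 to 0.539 (width 0.075). The correct width is 0.052 at ICC 0, 0.072 at 0.1, 0.101 at 0.3 and 0.123 at 0.5. At p = 0.9 the Poisson interval is 0.851 to 0.951 (width 0.100), against a correct width of 0.031 (ICC 0) to 0.074 (ICC 0.5).

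**Step 3: simulated coverage of the nominal 95% Poisson exact interval.** Beta-binomial data, 140 children, required doses uniform on 8 to 12, 4,000 runs per setting:

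| Coverage | ICC 0 | ICC 0.1 | ICC 0.3 | ICC 0.5 |
|---|---|---|---|---|
| 40% | 98.9% | 93.4% | 81.1% | 72.0% |
| 60% | 99.7% | 97.8% | 89.1% | 82.2% |
| 80% | 100% | 99.9% | 97.9% | 93.2% |
| 90% | 100% | 100% | 99.9% | 99.2% |

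A t interval on the mean child proportion gave 93.9% to 95.6% in every setting, including required doses spread over 3 to 15.

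**Step 4: comparison of two arms, if model-based errors were used.** At ICC 0 / 0.1 / 0.3 / 0.5, an unadjusted Poisson log-ratio test at nominal 5% had size 1.5 / 7.4 / 18.9 / 29.0% at coverage 40% and 0.0 / 0.2 / 2.0 / 6.8% at 80%. At 90% it was at most 1.0%. A log-link model on the child proportion with robust errors gave 4.1% to 5.6%.

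**Step 5: the other reading, one unit per child.** The Poisson variance becomes p/N, and the ratio becomes (1−p)[1+(m−1)ICC]/m. This never exceeds 1−p, so the interval is always too wide. With 140 children at 90% coverage it runs from 75.0% to 107.2%, an impossible upper limit; the exact binomial interval is 83.8% to 94.4%.

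**Step 6: dose weighting.** If coverage falls linearly with required doses, pooled ratio minus child mean = −slope × Var(m)/mean(m). For m uniform on 3 to 15, Var(m) = 14 and mean(m) = 9. A fall of 1 point per extra dose puts the pooled ratio 14/9 = 1.6 points below the child mean; a fall of 3 points gives 4.7.

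**The case against.** The named fault sits in the arm-level interval, not in the treatment contrast, which the SAP assigns to the regression. Poisson regression with robust child-level errors is a valid way to estimate a ratio of coverage, and robust errors may have been used and not reported. The test sizes in step 4 come from unadjusted comparisons, whereas the plan specifies a multivariable model; covariates that predict a child's coverage would lower the residual correlation. The largest sizes need low coverage, strong clustering and default errors together. At high coverage the error is mostly conservative and costs precision rather than false positives. Dose weighting hardly affects the contrast, because randomization gives the arms the same expected mix of required doses; it matters there only if the effect itself varies with required doses.

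All of this stands, and it limits the regression point to an unstated variance estimator and dose weighting to a side issue. It does not rescue the interval: that method is named explicitly, it does not match the outcome definition on either reading of the count, and no other text in the plan corrects it.

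**Conclusion.** The concern holds. That the Poisson exact interval is the wrong method for this outcome follows from the plan's own definitions, and confidence in it is high. Under the assumed ranges (140 children per arm, 8 to 12 required doses, ICC 0 to 0.5), the nominal 95% interval covers between 72.0% and 100% of the time. It tends to be too narrow at low coverage with strong clustering and too wide at high coverage with weak clustering. Because the plan gives none of p, m or ICC, the direction for this trial cannot be determined, and an effect on its conclusions is possible but not shown. Distorted test size in the regression depends on model-based errors having been used, which the plan neither states nor excludes.

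**What to change.** - Report each arm's coverage as the mean of the child proportions, with a child-level robust or bootstrap 95% interval in place of the Poisson exact one.
- Compare arms with a regression on the child proportion (fractional logit, or log-link Poisson on the proportion without a dose offset) using standard errors robust at child level. Adjusted and unadjusted results then target the outcome as defined.
- If a count model with log required doses as offset is kept, say that it estimates a dose-weighted ratio and use child-level robust errors. This is acceptable; changing the model is not essential.
- In every case, state the variance estimator.

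The cost is a re-analysis of existing data and revised methods wording. Intervals may widen or narrow, and point estimates may shift slightly where required doses differ between children.

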*Authentication and follow up:* The field staff were locally recruited and trained prior to the study. A pilot run of the software platform was performed at the study site in May-June 2016 to assess web and mobile-phone connectivity and to ensure that all operations performed optimally in real-time. At the start of the study, each mobile-phone was authenticated by a two-step process using an automated Short Message Service (SMS) verification code sent to the caregiver's mobile-phone during enrollment. The authenticated mobile-phone would receive a welcome message which was verified by the field worker. For the group receiving compliance-linked incentives, an additional authenticated step was utilized to ensure that mobile-phone on different carriers could receive automated incentives. The field worker identified the carrier by inspecting the mobile-phone screen or the SIM card and entering this information into the software platform. This immediately triggered delivery of mobile-phone talk-time equivalent to Indian Rupee (INR) 20 (~USD 0.33) to the caregiver's mobile-phone, which was then manually verified by the field worker. INR 30 (~USD 0.50) per completed immunization was provided subsequently to this group. Pre-scripted instructions were verbally provided at recruitment and at each follow up visit as follows: caregivers of children assigned to the control group were informed to come back for immunization at the next scheduled date, caregivers of children assigned to automated mobile-phone reminders alone were informed to come back for immunization on the date indicated by the automated mobile-phone reminder and caregivers of children assigned to automated reminders with compliance-linked incentives were informed to come back for immunization on the date indicated by the automated mobile-phone reminder, and that they would receive a specified amount of mobile-phone talk-time at the follow up visit.

*Biometric identification:* Biometric information (right index finger print) for the caregiver was collected at enrollment and verified by scanning the same finger seven times. In rare cases where the right index finger was not reliable, the right thumb, left index finger or left thumb was used in that order. Additional caregivers could be added during follow up visits and mobile numbers for caregivers could also be updated, but these procedures required the same verification process as described earlier.

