*Automated reminders and compliance-linked incentives:* For the study groups receiving automated reminders, SMS messages in the local language (Hindi) comprising the name of the child and the return date for the next scheduled immunization visit were sent. For the group receiving compliance-linked incentives an SMS message in Hindi stating that mobile-phone talk-time [in Indian Rupee (INR)] would be received on successful completion of the scheduled visit was sent simultaneously with the automated reminder. SMS messages were sent at 8:00 AM Indian Standard Time two days before and on the scheduled day of the immunization and messages were no longer than two sentences. For children who did not return on or before the scheduled date, two additional automated SMS reminders were sent the day after and seven days after the scheduled return date. At follow up visits, mobile-phone minutes equivalent to INR 30 (~USD 0.5) per completed immunization were provided in the compliance-linked incentives group. Immunizations received by a subject elsewhere during the study could also be added to the immunization records for both study groups and the control group, but compliance-linked incentives were only provided for immunizations registered by the software platform in the appropriate study group. Automated reminders were sent to all verified caregivers for a given child, but compliance-linked incentives were only provided to the primary caregiver's mobile-phone (identified during enrollment). All data transfers and compliance-linked incentives transactions were automated and occurred in real-time. We also calculated the cost in mobile-phone messaging and compliance-linked incentives. Since automated reminders were sent to multiple verified caregivers for each child, the costs for mobile-phone messaging (USD 0.0048 per message) was a cumulative of all messages send to all caregivers. However, compliance-linked incentives were only provided to the primary caregiver's mobile-phone and these costs were also included.

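### If the timeliness table counts doses, as its definition suggests, Fisher's exact test ignores that one randomised child can supply several, and its p-values are likely too small

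*Combined protocol and SAP*

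**What the plan says.** The Statistical Analysis Plan gives timeliness one sentence: "Comparison between groups for timeliness of immunization was calculated using the Fisher-exact test". It names no unit for the table and no allowance for repeated observations on a child. It also does not say whether the comparison is each test arm against control or one test across three groups.

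End Points treats its two outcomes differently. Coverage "was calculated for each child as the proportion of the total number of immunizations received" over the number required. Timeliness is "defined as the proportion of immunizations administered before or within 14 days after the scheduled date recorded during the study", with no per-child step.

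Study Procedures sets the unit of randomisation: "Eligible subjects were randomly assigned to one of three study groups". It also says that government staff gave a date for the following immunization visit whenever a child came back, that field workers entered it, and that the child's name with the caregiver's fingerprint "was used to ensure positive identification of individual children at every visit".

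**The concern.** Fisher's exact test treats every entry in the table as an independent observation. If the entries are doses, those from one child depend on the same caregiver and the same phone, and doses due at one visit may share a scheduled date. They will tend to be on time or late together. The table then holds less information than its dose count suggests, and chance differences between arms reach p<0.05 more often than 5% of the time.

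The reminders are tied to the scheduled date, so timeliness is an outcome on which they act directly. An overstated p-value here could support a claim that reminders or incentives improve punctuality when the data do not.

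**Working it through.** **Step 1: what does the table count?** A per-child proportion cannot enter a Fisher table unless each child is first classed as timely or not. The documents give no such rule. The definition supplies timely and late immunizations directly, so doses are the most natural unit. Visits are a second possibility, because Study Procedures says: "Each follow up visit was also correlated with the scheduled return date (if recorded in the system) of the administered immunization". Both sit below the randomised child.

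**Step 2: can one child supply several?** Yes, though no count is given. The best support is the new date given at each return visit (Study Procedures). The Authentication and follow up paragraph under End Points agrees: "Pre-scripted instructions were verbally provided at recruitment and at each follow up visit as follows". Study design and participants puts the recruitment target at February 11, 2017 and the end of the study at July 20, 2017. If recruitment stopped then, the last child had up to 17+31+30+31+30+20 = 159 days for repeat visits, and earlier children had longer.

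**Step 3: inputs for size.** The plan states no figure for timeliness to reproduce. Its 175 per group is for coverage and is used here only to set the number of children: 175 × 0.8 = 140 per arm after the 20% exclusion allowance. Timed doses per child (m), ICC and the timely proportion are all assumed.

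**Step 4: approximation.** Design effect DE = 1 + (Σm²/Σm − 1) × ICC. True error of a nominal 5% z-test = 2 × [1 − Φ(1.96/√DE)].
- Two doses each: DE = 1.1, 1.3, 1.5 at ICC 0.1, 0.3, 0.5, giving 6.2, 8.6 and 11.0%.
- One to three doses, equally likely: Σm²/Σm = 14/6 = 2.33; DE = 1.13, 1.40, 1.67, giving 6.6, 9.8 and 12.9%.
- One to six doses, equally likely: Σm²/Σm = 91/21 = 4.33; DE = 1.33, 2.00, 2.67, giving 9.0, 16.6 and 23.0%.

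**Step 5: simulation of Fisher's test itself.** Beta-binomial doses within child, two arms, no arm effect, 140 children per arm, 50% timely, two-sided p<0.05, at least 2,000 simulated trials per setting. Fisher's test is conservative, so its rates fall at or a little below the approximation.

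| Timed doses per child | ICC 0.1 | ICC 0.3 | ICC 0.5 |
|---|---|---|---|
| 1 | about 3–4% | about 3–4% | about 3–4% |
| 2 | about 5% | about 7% | about 9% |
| 1–3 mixed | about 5–6% | about 9% | about 12–13% |
| 1–6 mixed | about 9% | about 15% | about 23% |

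A test with robust variance clustered by child rejected in roughly 4 to 6% of trials throughout.

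**Step 6: effect on one result (invented counts).** Take two doses from each of 140 children, with 168/280 (60.0%) against 193/280 (68.9%) timely. Fisher p = 0.034. For a like-for-like comparison use the Wald test: difference 0.0893, SE = √(0.600×0.400/280 + 0.689×0.311/280) = 0.0403, z = 2.217, p = 0.027 with no clustering. Multiplying the variance by 1 + ICC gives:
- ICC 0.1: p = 0.035, 95% CI 0.006 to 0.172
- ICC 0.3: p = 0.052, 95% CI −0.001 to 0.179
- ICC 0.5: p = 0.070, 95% CI −0.007 to 0.186

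**The case against.** The strongest reply is that the unit is simply not stated. If the analysts classed each child once, or if nearly every child had a single timed dose, Fisher's test is valid. That stands. A reader might infer that the test is plainly wrong as written. The documents do not support that: they show an unstated unit, and the wrong test follows only on the dose or visit reading, though that is the more natural one.

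The evidence for several timed doses is also modest. The Automated reminders paragraph under End Points says "Immunizations received by a subject elsewhere during the study could also be added to the immunization records", but such doses need not carry a scheduled date in the platform. Dates counted only when recorded, follow-up was limited, and children up to 24 months could enrol. So timed doses per child may be few.

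A reader might take the 15 to 23% figures as the error rate of this trial. They are not: nothing in the documents supports up to six timed doses per child or an ICC of 0.5. With two doses and ICC 0.1 the inflation is negligible, because Fisher's conservatism offsets it. The invented example crosses 0.05 only because its counts were placed near the threshold. The simulation is two-arm, while the plan could mean one three-group test.

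What remains is that no passage deals with clustering on any reading in which a child enters the table more than once.

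**Conclusion.** The point holds in conditional form. Timeliness most naturally compares doses, possibly visits; children were randomised and can supply several. On that reading Fisher's p-values are likely too small. This rests on two assumptions: more than one timed dose for a material share of children, and positive correlation within child. The second is very plausible; the first cannot be checked from the documents. Under the assumed values the inflation runs from nothing (one dose, or two at ICC 0.1), through about 7 to 13% for two doses or a one-to-three mix at ICC 0.3 to 0.5, to higher rates only if children have many timed doses.

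The consequence is confined to one secondary outcome, which makes this worth correcting but not critical. It should not be read as either faulting or clearing the primary coverage analysis, which was not assessed here.

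**What to change.** 1. State the unit of the timeliness table (dose, visit or child), and whether the comparison is each test arm against control or one overall three-group test.
2. If the unit is doses or visits, replace Fisher's test with a logistic GEE using an independence working correlation and robust standard errors clustered by child. Report each test arm against control with a 95% CI. The observed timely proportions do not change; only their standard errors do.
3. If the unit is the child, state the rule that classes a child as timely and keep Fisher's test.
4. Whatever the unit, report the number of timed doses per child by arm, so that a reader can judge how much clustering matters.

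The cost is a few lines in the Statistical Analysis Plan and a different command in Stata, which is already in use. The platform identifies children at every visit, so no new data are needed. The downside is slightly wider intervals and larger p-values.
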